1. INTRODUCTION

During the first 12 weeks, pregnancy is carried out without significant blood flow from mother to the fetus. Later, fetal circulation in the developing tissues occurs at low oxygen pressure: in fetal blood, rarely pO₂ is higher than 30 mm/Hg. Therefore, from conception to delivery, the development of mammals occurs in hypoxia [1,2]. During delivery, infants are to cope with what could be defined as "*hyperoxic challenge*". The oxidative stress, that is the imbalance between oxidants and antioxidants in favor of the formers, affects tissues by producing free radicals. Extremely low birth weight infants (ELBW, birth weight lower than 1000 grams) are particularly sensitive to the oxidative stress, because of the immaturity of the antioxidant metabolic systems as well as the existence of frequent comorbidities, especially infections that, on their turn, increase the oxidative stress [3]. All the pathologies caused by the oxidative damage are defined as "oxidative stress-related diseases in newborns" [4,5]. These disorders, that are generally developed at the same time by the patient, include bronchopulmonary dysplasia (BPD), retinopathy of prematurity (ROP), necrotizing enterocolitis (NEC), periventricular leukomalacia (PVL) and, at least partially, intraventricular hemorrhage (IVH) [4,5]. EPICure (Extremely Premature Infant Cure) studies carried out in the United Kingdom showed that among premature infants born between the 22nd and the 26th gestational week, and with a postmenstrual age of 26 weeks, 68% of those who survived developed BPD, 21% were affected by ROP at least in one eye and 13% presented serious alterations during brain ultrasound scans [6,7]. Most recent papers described red blood cell transfusions as a main risk factor for the development of these pathologies [8-14] and the overall survival [14-16]. There are various factors explaining the correlation between the number of transfusions and the seriousness of the pathologies due to the oxidative damage, such as the immune modulatory effect (the term "transfusion-related immunomodulation" is used for the transfusion-related immunosuppression syndrome) [17,18] or the inflammation caused by "micro particles" that are released during the storage of red blood cells [19-21]. However, it is increasingly evident the role played by adult hemoglobin (HbA) that, due to its lower affinity to oxygen than fetal hemoglobin, greatly contributes to the oxidative stress [13,22,23]. The harmful role of HbA in preterm has clearly emerged in a recent prospective study, which showed that the incidence of ROP was inversely related to patients' fetal hemoglobin (HbF) levels, with a higher incidence among those showing the lowest levels [13]. In these patients, the level of HbF was obviously inversely proportional to that of HbA [13]. The current neonatal transfusion guidelines, by the Italian Society of Neonatology and the Italian Society of Transfusion Medicine, recommend the use of fresh leukoreduced red cell concentrates and the irradiation of blood components [24].

However, it seems that at present these precautions are not able to reduce the incidence of the oxidative damage-related pathologies [25, 26].

Nonetheless, transfusions of red cell concentrates continue to be a life-saving therapy and they are fundamental to treat the anemia of preterm infants. Anemia in preterm infants, compared to the physiological anemia in full-term newborns, is characterized by a faster and more serious decline in the levels of hemoglobin (Hb) and hematocrit (Hct). The repeated venous samplings for laboratory tests, the lack of nutrients, the insufficient production of endogenous erythropoietin, associated to the concurrent infections and to the possible blood losses, further exacerbate the anemia of prematurity [27-32]. In spite of the numerous precautions, such as the increasingly reduced volumes of samplings, the reduction of transfusion limits and the widespread use of iron and erythropoietin, the transfusion of 20 ml/kg of red cell concentrates is inevitable in almost 90% of ELBW patients [30-32]. Since in ELBW preterm infants anemia is particularly relevant during the first weeks of life, they all receive most transfusions before the 32nd week of PMA [14-16, 25].

Compared to the adult donor blood, cord blood taken from placenta and umbilical vessels has some important characteristics in terms of neonatal transfusions. As a matter of fact, cord red cells contain HbF, which is more physiological than HbA in preterm infants because of its higher affinity to oxygen. Moreover, the immune and infection profile of cord blood is absolutely “naïve”, as shown by the years of experience with hematopoietic transplants [33]. All these characteristics are a valid reason for using it when transfusing preterm infants. The use of autologous or allogeneic umbilical cord blood as an alternative to the transfusion of adult red cells was greatly confirmed by literature to the point that cord blood red cell concentrates were included by the Italian National Blood Center in the blood components acknowledged by the UNI 10529:1996 norm that regulates their traceability (umbilical cord blood red cell concentrates, UCB-RBC, blood component 73). These units can be irradiated like those obtained from adult donors. In a recent study, we tested the ability of the UNICATT Cord Blood Bank to cover the transfusion needs of low birth weight infants who were admitted to the Neonatal Intensive Care Unit (NICU) of our hospital with red cell concentrates from cord blood [46]. The study included patients who were born before the 30th week of gestation and/or with a birth weight lower than 1,500 g and who needed transfusions during the first 28 days of life. After the first transfusion event, each patient was assigned to the treatment arm (umbilical cord blood-packed red cells, UCB-RBC) or to the control arm (adult donor red cell concentrates, A-RBC), depending on the availability of UCB-RBC of the same blood type (ABO-Rh). From March, 1 to February, 28 2014, 20 patients out of the 63 that were hospitalized in the NICU were included in our study. Out of 20 infants, 9 were transfused with UCB-RBC and 11

with A-RBC. Overall, we transfused 23 UCB-RBC units and 27 A-RBC units. We observed that the two types of blood components led to a similar increase in the hematocrit levels and that the patients that were transfused with UCB-RBC or A-RBC received a similar number of transfusions at similar time intervals. There were no adverse events nor transfusion reactions and no CMV infections were recorded. In this limited number of patients, with an average follow-up of 57 days, the incidence of prematurity-related pathologies appeared to be globally comparable [46]. However, it was interesting to notice that the only two patients who did not develop ROP were only transfused with UCB-RBC [47]. More recently, a prospective study was carried out to show that the incidence of ROP was related to the levels of HbF in patients: the lower the levels, the greater the incidence [13]. Among those patients, the level of HbF was obviously inversely proportional to that of HbA. Therefore, even if it was a limited number of patients, the absence of ROP among the patients who were transfused with umbilical cord blood indirectly confirms the potentially damaging effect of adult blood transfusions [46, 47]. Our feasibility study also demonstrated that with current resources we are able to cover 50% of these patients' transfusion needs [46].

At global level, the implementation of a program for the transfusion of cord blood in a preterm infant could have an important clinical impact. Additionally, the introduction of this transfusion strategy could be an advantage in the rationalization of resources when using blood components. Actually, according to the criteria of cellularity established by the Italian Bone Marrow Donor Registry (IBMDR), less than 10% of cord blood units are cryopreserved and listed for transplants [48].

2. OBJECTIVES OF THE STUDY

The objective of the study is to investigate the correlation between the levels of HbF and the use of umbilical cord blood red cell concentrate transfusions in ELBW preterm infants and/or infants who were born before the 30th week of gestational age (GA). Since transfusions are one of the main mechanisms to reduce HbF, they will be carried out with umbilical cord blood red cell concentrates (UCB-RBC). Our objective is to demonstrate that UCB-RBC transfusions, until the 32nd week of PMA, guarantee average levels of HbF that are higher than in adult-RBC (A-RBC) transfusions. The following outcomes were defined:

Primary outcome:

- Average levels of HbF at 32nd week of PMA in patients receiving different transfusion support.

Secondary outcomes:

- To show that UCB-RBC transfusions are not less effective than A-RBC transfusions, as for the post-transfusion increase in the hematocrit and the interval between two transfusions.
- To show the association between average levels of HbF during the inpatient stay and comorbidities (ROP, BPD, NEC, PVL and IVH) or deaths occurred within 36 weeks of PMA.

3. EXPERIMENTAL DESIGN

3.1 Study design. This study is a prospective non-randomized study to evaluate the correlation between the reduction in the level of HbF (based on the relation between HbF and HbA) before the 36th week of PMA and the type of transfusion (UCB-RBC or A-RBC).

3.2 Duration of the study. The study will have an overall duration of one year. The enrollment of patients will last 10 months. Considering the volume of activity of our NICU and the type of eligible patients, such a period of time was considered adequate to enroll the number of patients necessary to reach the established objectives. As for the transfusions (UCB-RBC or A-RBC), the intervention phase will last from the enrollment to the completion of the 32nd week of PMA, while the weekly monitoring of HbF will continue until the completion of the 36th week of PMA.

3.3 Early study termination. The study will be terminated with the occurrence of adverse events that can be risky for the patients or if the Proposer thinks it is necessary, based on the evaluation of safety data.

3.4 Study termination. The study will be considered over when the collected data make it possible to draw up the final report.

3.5 Study endpoints.

- HbF levels before and after each transfusion;
- Average HbF levels (at 32 weeks of PMA; at last control)
- Prevalence of ROP and/or BPD and/or NEC and whatever health problems (infectious pathologies, hemorrhages including IVH, kidney failure, thromboembolism, surgical complications, etc.) before the 36th week of PMA;
- Transfusion efficacy of UCB-RBC compared to A-RBC (all transfusions before the 36th week of PMA, evaluated based on a) average time interval between two subsequent transfusions and b) average increase in the post-transfusion capillary hematocrit (Δ Hct).

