5.4 The collection of cord blood will be carried out in the birth centers that are part of the Cord Blood Bank, according to the procedures used by the Bank itself. The collected units will be adequately conserved at low temperatures (2-6°C) and fractionated within 24 hours. The units that are not eligible for transplant because of low cellularity (total nucleated cells <1,200 x 10⁶), with a volume >60 ml excluding the anticoagulant (CPD, Citrate, Phosphate, Dextrose), without clots and/or hemolysis, will be considered eligible for fractionation to obtain UCB-RBC. Eligible UCB units will be fractionated by an automatic blood component processing system (the UNICATT Cord Blood bankl will use Compomat[®] G4 by Fresenius HemoCare GmbH, D-61346, Bad Homburg, Germany). Red cell concentrates will be resuspended in a preservative solution containing adenosine, glucose and mannitol (SAGM, ratio red cell: SAGM = 2:1) and filtered with the filter Purecell[®] NEO Neonatal High Efficiency Leukocyte Reduction Filter (Pall, East Hills, NY, USA) to remove leukocytes. Blood cultures for bacteria and fungi will be set up. Only the units that tested microbiologically negative will be considered eligible for transfusion (blood cultures, molecular and serological tests for HCV, HBV, HIV and syphilis). UCB-RBC units will be stored at a temperature of 2-6°C for 14 days, in order to allow the γ -irradiation (¹³⁷Cs) when they are assigned to the patient.

5.5 Transfusion request. Units will be requested according to the procedures established by the Blood Transfusion Service, based on the current legislation and in accordance with the guidelines reported in Annex III. When a blood request arrives, the hematologist on duty at the Blood Transfusion Service will check if the patient's name is included among those enrolled in the study and the date of completion of the 32nd week of PMA; then he/ she will identify ABO-Rh(D) units to transfuse (UCB-RBC if available, otherwise A-RBC). The transfusion dose will be determined regardless of the type of blood component being used and will be established according to the criteria generally implemented in the NICU. The UCB-

RBC and A-RBC units will be transfused within six hours in order to reduce functional alterations of red cells and the risk of microbial contamination.

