5.6 Monitoring of transfusion need. All the transfusions carried out in all the patients before the 36th week of PMA will be recorded. Before and after every transfusion, HbF, HbA and capillary arterial-blood gas will also be tested. Blood samples for CBC and/or reticulocytes will only be taken if clinically necessary and not for study-related reasons.

5.7 Monitoring of HbF and HbA levels. Three capillary blood samples will be taken every week for dosing HbF and HbA. If other tests for routine assistance, or for blood units cross-match, are carried out, part of the blood sample will be recovered for dosing HbF and HbA. The dosage will be carried out on samples that were stored at the Hematology Service of the Foundation, through HPLC on lysate samples. This procedure needs very low sample volumes (50-100 µL).

5.8 Definition of the prematurity-related pathologies (ROP, BPD, NEC and IVH). ROP (grade I-IV) will be diagnosed based on the criteria of the “International Committee for the Classification of Retinopathy of Prematurity” [49]; NEC will be diagnosed based on the criteria of Bell [50]; BPD is diagnosed when an infant continues to need additional oxygen after 28 days of age, at the 36th week of PMA [51]; the diagnosis of IVH will be based on the criteria of Papile [52].

5.9 Recording of clinical data and laboratory parameters. For each patient, the following parameters will be recorded on specific case report forms: GA and birth weight, sex, ethnicity, twin birth, PMA, respiratory support, additional oxygen, length of the hospitalization in the NICU, number of days under antibiotic therapy and PMA when leaving the hospital. All the causes of mortality and morbidity occurred within the 36th week of PMA will be recorded (infectious episodes, hemorrhagic events, kidney failure, thromboembolism, surgical complications, etc.). All the possible adverse events occurred within that date would also be recorded (for example, the unexpected adverse events, including all the alterations of the laboratory parameters, regardless of their seriousness). All the hematological (Hb, HbF% and HbA%, Hct) and transfusion data (date, number of transfusions, type of transfusion, volumes of transfused RBC) will also be recorded. For all those patients who were discharged before the completion of the 36th week of PMA, the clinical evaluation, the determination of HbF on capillary blood and the collection of data will be carried out at ambulatory level.

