6. STATISTICAL CONSIDERATIONS

6.1 Definition of analysis sets

- **Enrolled (E) set or Intent-to-treat (ITT) analysis.** It will comprise all the enrolled patients, regardless of the administration or not of RBC transfusions.
- **Treated (T) set.** This group will comprise all the patients who were at least administered one transfusion, regardless of the completion of the observation period (36th week of PMA). Excluded from this set are the enrolled patients who were not transfused.
- **Per-Protocol (PP) set.** This group will comprise all the transfused patients who completed the observation period (36th week of PMA) or who died after completing it.

6.2 Calculation of sample size. The main goal of the study is to correlate the average HbF levels to the type of transfusion (UCB-RBC or A-RBC). With a population of 25 patients that will be studied during the following 8 weeks and a mortality rate of 1.9 patients/month, we expect to have 196 weekly doses of HbF to correlate to 98 transfusions. The total expected number of transfusion from birth to the completion of the 36th week of PMA was calculated to be around four transfusions per patient, with an UCB-RBC:A-RBC ratio of 1:1. In fact, for those patients with birth-determined characteristics similar to those of the studied population, the average number of transfusions within the 36th week of PMA is around 4 transfusions/patient [25], while in our previous study the average number of transfusions was 3 ± 1.7 [46]. In accordance with the literary data, preterm infants have an expected HbF concentration between 85% and 90% at birth and between 70% and 75% at the 36th week of PMA [54]. We expect that for the newborns who will not be transfused the HbF levels will stay in this range (70%-90%), while for the patients who will be transfused with adult red cells, HbA will dilute HbF. Even though there are no literary data yet, if we know the volume of transfused red cells (20 ml/kg) and the patient's blood volume, we can also assume that, for every adult red cell transfusion, HbF will be reduced by 15-20% compared to the pre-transfusion values until reaching levels lower than 20% among those patients who were transfused more than 4 times with adult blood.

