6.3 Statistical data analysis. The continuous variables will be expressed as mean (\pm SD) or as median (interquartile ranges, IQR); all deviations from normality will be detected with the Shapiro-Wilk test. The categorical variables will be expressed as n, (%), percentage). HbF levels in different type of transfusions will be compared in univariate analysis Mann-Whitney U test, end Kruskall Wallis test). Similarly, the transfusion efficacy analysis will be carried out based on a UCB-RBC and A-RBC non-inferiority study design by comparing the average time interval between two subsequent transfusions and the average post-transfusion capillary Ht

increase (Δ Ht) (Mann-Whitney U Test). The transfusion sample included in the study makes it possible to detect a difference between groups that is equal to at least 1 standard deviation with type I error $\alpha = 0.05$ and type II error $\beta = 0.2$ and a medium effect size (0.6). The correlation between the type of transfusion and other variables (prematurity related pathologies) will be tested using Fisher's exact test. Secondarily, in order to evaluate the effect of HbF reduction on the onset of prematurity-related pathologies, the levels of HbF levels will be inserted in a multiple linear regression model, by expressing the correlation between the onset of prematurity-related pathologies and the variables in terms of odds ratios (ORs \pm 90% confidence interval).

6.4 The primary outcome analysis will be tested on "E", "T" and "PP" sets. Transfusion efficacy outcome will be tested on "T" and "PP" sets.

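### The transfusion-interval comparison (2, 3.5, 6.3) has no rule for open intervals, product attribution or clustering, so a true UCB-RBC deficit would be understated; the comparison window (week 32 or 36) also needs reconciling

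*Combined protocol and SAP*

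**What the plan says.** Section 2 aims to show that UCB-RBC is no less effective than A-RBC on the hematocrit rise and on "the interval between two transfusions". Section 3.5 takes "all transfusions before the 36th week of PMA, evaluated based on a) average time interval between two subsequent transfusions". Section 6.3 describes a "non-inferiority study design by comparing the average time interval between two subsequent transfusions", with a Mann-Whitney U test, and 6.4 applies it to the Treated and Per-Protocol sets.

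Product is chosen at each request: "UCB-RBC if available, otherwise A-RBC" (5.5). Section 6.2 sets the scale: "With a population of 25 patients that will be studied during the following 8 weeks and a mortality rate of 1.9 patients/month", 98 transfusions, about four per infant, "with an UCB-RBC:A-RBC ratio of 1:1".

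No section says what to do with the time from an infant's last transfusion to week 36, death or loss. None says which product an interval belongs to when its two transfusions differ, and none allows for several intervals from one infant. Section 6.3 states no non-inferiority margin.

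On the window, 3.5 and 6.2 count transfusions to week 36, and 5.6 records them that far: "All the transfusions carried out in all the patients before the 36th week of PMA will be recorded". Sections 2 and 3.2 tie the transfusion intervention to week 32, and 5.5 has the hematologist check that date before choosing a unit. Section 5.2 labels the week-32 date as the end of the A-RBC phase only. No section states which product is given in weeks 32-36.

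**The concern.** An interval defined by two transfusions is observed only if the second one happens. Each infant's last transfusion contributes nothing to this endpoint, and an infant with a single transfusion contributes nothing at all. A long interval is more likely than a short one to be cut off by week 36 or death. More intervals are therefore lost after the longer-lasting product, and any true difference is pulled towards zero. For a claim that UCB-RBC is not worse, pulling a real deficit towards zero is the unsafe direction.

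Attribution matters just as much. When product changes from one request to the next, the interval can be credited to the transfusion before it or the one after it. Only the first choice measures how long a product lasts.

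The window is a separate question. If the products are compared only to week 32 and later transfusions enter under one product, product and postmenstrual age are mixed.

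**Working it through.** **1. The plan's own count.** Section 6.2 gives 98 transfusions and 196 weekly HbF values. Both follow from 24.5 infants: 24.5 × 4 = 98 and 24.5 × 8 = 196. With 49 per product, a two-sided 0.05 test and Mann-Whitney efficiency 0.955, power at 0.6 SD is Φ(0.6 × √(49 × 0.955 / 2) − 1.96) = Φ(0.94) = 83%. That agrees with the stated β = 0.2. The same sentence of 6.3 also names "a difference between groups that is equal to at least 1 standard deviation", at which power would be 99.8%.

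**2. Open intervals.** Each transfused infant has one last transfusion. With all 25 transfused, 98 − 25 = 73 intervals close and 25 of 98 (26%) stay open.

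**3. Mixed intervals.** If each transfusion is independently 50:50 (assumed; 6.2 gives only the overall ratio), an interval has different products at its two ends with probability 2 × 0.5 × 0.5 = 0.5. That is about 36 of 73.

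**4. Direction, by hand.** Take exponential intervals with mean m and R days left to week 36. The share left open is p = exp(−R/m), and the mean of the completed ones is m − R·p/(1 − p). Assume A-RBC m = 16 days and UCB-RBC m = 12 days (25% shorter, true deficit 4 days).

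| Days left | Open, A / UCB | Completed mean, A / UCB | Deficit seen |
|---|---|---|---|
| 49 | 4.7% / 1.7% | 13.60 / 11.16 | 2.44 (61%) |
| 28 | 17.4% / 9.7% | 10.11 / 8.99 | 1.12 (28%) |

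**5. Size, by simulation.** Inputs from 6.2 are 25 infants, 56 days, 1.9 deaths per month (1.9 / (25 × 30.4) = 0.0025 per infant-day), 3.92 transfusions per infant (98 / 25) and product 1:1. The other inputs are assumed:
- first transfusion exponential with mean 7 days, before day 28;
- gamma intervals with shape 1, 2 or 3;
- lognormal infant effect with variance 0 or 0.15;
- A-RBC mean interval of 14.3-18.6 days, set so that equal products give 98 transfusions;
- UCB-RBC intervals 25% shorter, each credited to the transfusion that starts it.

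Results:
- Open intervals: 19-20% after UCB-RBC, 25-26% after A-RBC.
- Mean deficit of 3.6-4.1 days is seen as 1.6-2.8 days (38-79%).
- Median deficit of 2.6-3.2 days is seen as 1.3-2.6 days. The Kaplan-Meier median, with open intervals censored, recovers it within about 0.04 days.
- Changing the mean time to first transfusion to 3 or 14 days, with or without deaths: 36-68% of the mean deficit is seen.
- Equal products: no bias.

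**6. Attribution.** In the same simulation, crediting each completed interval to the product that ends it leaves a difference within about 0.04 days of zero.

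**7. Error rates, illustrative only.** Section 6.3 gives no margin, so one was set equal to the assumed 25% deficit, at one-sided 2.5%. The Mann-Whitney confidence limit on completed intervals then declares non-inferiority in 6.5-10.5% of studies. With a 10% deficit the figure is 3.6-4.6%. A different set of assumptions (A-RBC mean 14 or 18 days, no deaths, confidence limit on the mean difference, not all settings calibrated to 98 transfusions) gives 7-35%, against 3-7% if every interval were seen in full.

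**8. Window.** Suppose only A-RBC entered the comparison after week 32 and the products were equal. One set of assumptions gives A-RBC intervals shorter by 0.01-0.09 SD; another gives a UCB:A interval ratio of 1.05-1.27. The inputs that decide between them (the late share of transfusions, how need changes with age, the product given late) are not in the documents.

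**The case against.** The plan never says that only completed intervals count. That is correct: it is an inference from the definition. But a Mann-Whitney test on intervals so defined has nothing else to use, and no rule brings in the open ones.

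A reader might also infer that the defect costs power, since 73 intervals in place of 98 lowers nominal power at 0.6 SD from 83% to 71%. That should not be counted as harm. A time-to-next-transfusion endpoint never had 98 events, the censored analysis has the same 73, and the figures assume independent transfusions and a test for difference.

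The 25% deficit is assumed. Section 1 reports that the two products were transfused at similar intervals in the feasibility study (20 infants, non-randomized). With equal products there is no bias, and a true UCB-RBC advantage would shrink as well, which is the cautious direction. This stands: the problem arises only if a real deficit exists. A non-inferiority analysis, however, has to be able to detect one.

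The shrinkage also depends on crediting intervals to the starting transfusion, which the plan does not specify. That stands too, and it makes the missing attribution rule as basic as the missing censoring rule.

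On the window, an endpoint may outlast the intervention phase, and 3.5 states week 36 explicitly. The passages are therefore unclear together, not strictly contradictory.

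**Conclusion.** The concern holds for this secondary outcome and should be corrected before analysis. Followed as written, 3.5 and 6.3 leave out about a quarter of the intervals, and the loss depends on their length. With attribution to the starting product and an assumed 25% deficit, roughly 40-80% of the mean deficit would be seen. With attribution to the ending product, almost none would be. The direction is firm under starting-product attribution and a fixed window. The size rests on assumed interval distributions that the documents do not give.

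Two stronger readings are not supported. No particular false non-inferiority rate can be assigned to the plan, because 6.3 sets no margin and the rates in the working move widely with the assumptions. Nor do the documents show that product and age are in fact mixed after week 32, or whether any such mixing would be small or large.

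**What to change.** In 3.5 and 6.3, define the endpoint as time from each index transfusion to the next, credited to the index product. Censor open intervals at week 36 or loss to follow-up. Censor at death in the main analysis, and add a sensitivity analysis with death as a competing event, because sicker infants may both die and need more transfusions. Report, for example, the Kaplan-Meier median or the restricted mean to 28 days by product, with variance clustered by infant. Cluster the hematocrit comparison by infant as well. Any margin should be stated on the scale chosen.

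The near-exact recovery in the simulation assumes constant transfusion need and death unrelated to need. Section 1 says most transfusions fall before week 32, so some dependence may remain.

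The cost is new wording and slightly more analysis work. No new data are needed: transfusions are recorded to week 36 (5.6), and infants discharged early are followed to then (5.9). All 98 transfusions contribute, as 73 events plus 25 censored times, with no gain in events.

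Separately, reconcile 2, 3.2, 3.5, 5.2, 5.5 and 6.2 on the period in which the products are compared. If it runs to week 36, the window in 3.5 can stay. If it ends at week 32, limit the efficacy comparison to index transfusions up to then, report later ones descriptively, and restate the count and the 1:1 ratio in 6.2. That has a price. If 10-30% of transfusions are late (assumed), 98 × 0.9 = 88 to 98 × 0.7 = 69 remain for the hematocrit rise. If 14-31% are late, about 60-70 observed events remain for the interval.
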